3.2 Primary Study Endpoints

Percent Kilocalories Obtained Orally will be the primary study endpoint. This measure will be obtained using the three day 24 hour food recall. The 24hr food recall is a standardized five-pass method, developed by the US Department of Agriculture for use in national dietary surveillance. Although there are weaknesses to every method of dietary assessment, this one was selected as it is widely used in several large trials and data suggest it is the most valid and reliable method of dietary assessment for children (35) The data will be collected using highly standardized probes by trained research staff, and parents will be presented with paper food models and measuring devices prior to interviews to reference during the recall. Recalls will be analyzed with the Nutritional Data System for Research, version 2016; University of Minnesota, Minneapolis, MN. Although a plethora of information is available from this analysis, the current study will focus on total daily oral calorie intake. This measure will be completed the week following Clinic Visits at weeks 0, 10, 14 and 24.

3.3 Secondary Study Endpoints

Parent stress and parent and child quality of life will be the secondary study endpoints and be completed by parents at Clinic Visits at weeks 0, 10, 14, and 24.

1. Parent Stress (The Pediatric Inventory for Parents – PIP36). Parent stress will be measured via the Pediatric Inventory for Parents, a 52 item parent questionnaire developed to measure parent stress around caring for a medically complicated child. The measure has a total and four domain scale scores (communication, medical care, role function, emotional function). For the purposes of the current study, we will use only the total score. The measure has been shown to be a valid and reliable measure of pediatric illness-related parenting stress (36).
2. Child Health-Related Quality of Life (Infant Toddler Quality of Life – ITQOL47). Child quality of life in children <5 years old will be measured with the Infant Toddler Quality of Life short form questionnaire, validated for children 2 months through 5 years of age. The ITQOL has 47 items which result in 9 multi-item scales with well-established reliability (Cronbach's alpha > .70) and validity. Similar to our previous work (11), we will use the multi-item scales in our analyses.
3. Child Health-Related Quality of Life (Child Health Questionnaire Parent Form – CHQ-PF50). Child quality of life in children \geq 5 years old will be measured with Child Health Questionnaire Parent Form questionnaire. The parent-reported CHQ is normed for ages 5-to-18 and measures 14 unique physical and psychosocial concepts. The CHQ has 50 items and scores for the parent-reported versions can be analyzed at the concept level (CHQ Profile Scores) or combined to derive an overall physical and psychosocial score, (CHQ Summary Scores).
4. Parent Quality of Life (SF-36v2). Parent Quality of Life will be measured with the widely used Parent Quality of Life Short Form 36, version 2. Over 4000 studies have used the SF-36, making it a widely accepted measure, and v2 has improved reliability ($\alpha = .73-.90$), and validity (38). The 36 questions with 5 point scales have 8 scaled scores: vitality, physical functioning, bodily pain, general health perceptions, physical role functioning, emotional role functioning, social role

CONFIDENTIAL

This material is strictly confidential and is intended solely for the guidance of clinical investigation. Do not disclose or use except as authorized in writing by the study sponsor

functioning and mental health. As is typical, we will convert individual scores to z scores, resulting in a standardized combined score (39). This standardized combined score will be used in analyses, as well as specific subscales that previous research indicates may be sensitive to the current intervention (Growth and Development, Behavior, General Health Perceptions, Parental Impact: Emotion, Parental Impact: Time).

5. Impact of Pediatric Chronic Health Conditions (PedsQL 2.0, Family Impact Module). The impact of pediatric chronic health conditions on parents and the family will be measured with the PedsQL 2.0, Family Impact Module (63). This 36-item survey measures parent self-reported physical, emotional, social, and cognitive functioning, communication, and worry. In addition, the Module assesses parent-reported family daily activities and family relationships.
6. Patient Health Questionnaire-9 (PHQ-9). The Patient Health Questionnaire (PHQ)-9 is a 9-item measure of depressive symptoms. It is used to provisionally diagnose depression and grade severity of symptoms in general medical and mental health settings. Scores each of the 9 DSM criteria of MDD as "0" (not at all) to "3" (nearly every day), providing a 0-27 severity score. This measure asks about the parent's thoughts of suicide or self-injury. Study staff will view the responses to this measure within 3 days of the measure being completed. If a parent indicates suicide or self-injury ideation on the measure, the Lead Site PI who is a licensed child psychologist will be notified. The Lead Site PI will then contact the parent to decide if a referral to local support centers is necessary.
7. General Anxiety Disorder-7 (GAD-7). The GAD-7 is a 7-item screening tool and symptom severity measure for the four most common anxiety disorders (Generalized Anxiety Disorder, Panic Disorder, Social Phobia and Post Traumatic Stress Disorder). Higher GAD-7 scores correlate with disability and functional impairment.
8. Impact of Event Scale – Revised (IES-R). The IES-R is a 22-item self-report measure (for DSM-IV) that assesses subjective distress caused by traumatic events. It is a revised version of the older version, the 15-item IES (Horowitz, Wilner, & Alvarez, 1979). The IES-R contains seven additional items related to the hyperarousal symptoms of PTSD, which were not included in the original IES. Items correspond directly to 14 of the 17 DSM-IV symptoms of PTSD. Respondents are asked to identify a specific stressful life event and then indicate how much they were distressed or bothered during the past seven days by each "difficulty" listed.
9. Demographics. Families will complete a demographic questionnaire regarding age, race, ethnicity, income, free/reduced lunch status, and parental education, along with a medical history questionnaire asking about diagnoses at birth and diagnoses at week 0. These variables will be used to describe our sample and in any covariate analyses
10. Gut microbiota. Stool will be collected at each of the 4 clinic visits (Weeks 0, 10, 14 and 24). Once participants are consented, they will be provided with a toilet hat and sterile cup for stool collection. Once collected, stool will be stored in the sterile collection cup in the participant's freezer, until it is transferred or shipped on ice to a -80° C freezer at the study site. Each sample will be labeled with less than 8 characters and each label which matches the participant ID and will start with a letter (labels may not start with a number; per Novogene guidelines). Micro tubes will be shipped on dry ice to Novogene, where samples will undergo 16s rDNA sequencing utilizing HiSeq PE250. Sequencing will occur in the V4 region with primer 515F and 806R. Data output will be 100,000 raw reads per sample.
11. Clinical care measures. Height, weight, and vital signs will be obtained at clinic visits 1-4. These measures are routine clinical care, but will the data will be used for research purposes.

CONFIDENTIAL

This material is strictly confidential and is intended solely for the guidance of clinical investigation. Do not disclose or use except as authorized in writing by the study sponsor

12. Tube Feeding Parent Report. Some participants may receive tube feedings after the protocol dictates that they should be fully weaned due to an unsuccessful tube feeding wean or an acute illness where the child needs to temporarily resume tube feedings. Caregivers who are giving tube feedings after the weaning phase of the protocol at Week 12 will be asked to self-report the amount of tube feeding their child is receiving. The survey is four questions and asks parents to report the volume of formula given, the approximate % of total calories from tube feedings, and the reason tube feedings were given. The survey will be sent to parents daily while the participant is receiving tube feedings. Once the participant is no longer receiving tube feedings, they will not be asked to complete the survey.

Post-Intervention Survey and Qualitative Interview. The study team will conduct an online survey and qualitative interviews over the phone with parents of children who have completed the intervention. Parents who choose to participate will be verbally consented over the phone. The survey ask parents will also be asked to self-report their child's current height, weight, and tube feeding status. The 1-hour interview will ask parents about their experience of having a child with feeding issues, opinions regarding the iKanEat intervention, the health coaching, and the tube wean transition. Parents will be paid \$20 for completing the online survey, and up to \$80 for the phone interview. In total, parents may receive up to \$100 via an electronic Amazon gift card. De-identified structured interview audio recordings will be transcribed by a professional transcription service.

13. Other considerations. All children already receiving intensive feeding therapy will be excluded (see Participant section). Participants will continue treatment with their multidisciplinary feeding teams (typically 6-10 weeks between visits at our participating sites) and any other therapies throughout the 24 week intervention protocol. Because these children are medically complicated, often with deficits in many areas, this is important for the welfare of the children. Therapies outside of the iKanEat protocol will be assessed via the post-treatment questionnaire at the final clinic visit (week 24) and be available for use in analyses as covariates if necessary. Also, once the study is completed and all measures are turned in to the study team, participants will be unblinded by the statistical team, informed of their group (megestrol/placebo) and scheduled for follow up care with their multidisciplinary feeding team as appropriate.

3.4 Primary Safety Endpoints

Safety Interviews

To monitor for negative side effects, patients will be interviewed during clinic visits and tele-visits for any negative gastrointestinal, behavioral, feeding, or other negative sequela suspected to result from our treatment. Participants will be asked to measure the child's weight using a digital home weight scale during tele-visits to monitor changes in weight.

Subjects will be considered “at risk” and reviewed by the medical monitor and site PI if either of the following two conditions. The medical monitor and site PI will determine if it is safe for the participant to continue in the study (or, under what conditions it may be safe for the participant to continue) given all patient characteristics, including baseline weight for height ratio or BMI percentile.

- 1) If more than 0.5 kg of weight is lost consistently per week over three consecutive weeks
- 2) If the subject experiences 10% loss of total body weight

If any negative outcomes are identified they will be reported to our Data Safety and Monitoring Board and proper steps will be taken.

CONFIDENTIAL

This material is strictly confidential and is intended solely for the guidance of clinical investigation. Do not disclose or use except as authorized in writing by the study sponsor

Children will also have laboratory measurements to assess megestrol safety.

- 1) Morning Cortisol. The blood for the morning cortisol test will be drawn before 8am by the local laboratory or mobile phlebotomy services to test for adrenal insufficiency. The test will take approximately 1 mL of blood and will be drawn at weeks 10 and 14 for all subjects. Participants taking inhaled or intranasal steroids will take an additional blood draw at week 0. If an abnormal value is measured, a repeat morning cortisol level will be obtained. Every effort should be made to complete a redraw at the earliest convenience, within 7 days. The medical monitor will be on the weekly team calls, so she will be able to advise based on specific circumstances. If the 2nd test is also abnormal, the study protocol will be paused, and a pediatric endocrinologist will be consulted to determine if a formal in-person consultation is needed with endocrinology. The subject may either resume the protocol or be removed from the study pending the endocrinologist and study team's assessment.

4 Subject Selection and Withdrawal

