1.4 Dose Rationale and Risk/Benefits

The dose of the megestrol was based upon the preliminary clinical data published.

CONFIDENTIAL

This material is strictly confidential and is intended solely for the guidance of clinical investigation. Do not disclose or use except as authorized in writing by the study sponsor

2 Study Aims

The primary aim of the current study is to conduct a randomized controlled trial of a 4-week course of megestrol, the only remaining medication that is part of the iKanEat protocol, to ensure that the addition of megestrol results in improved child outcomes. The second aim is to assess the safety of megestrol as part of the iKanEat protocol. Our previous work (as well as work by others) suggests that a 6 week course of megestrol can lead to adrenal insufficiency in some children (11-14), so as part of the current protocol, we will assess the safety of a 4 week course of this drug.

Finally, parents of tube fed children encounter multiple psychosocial stressors regarding tube feeding (15). These include concerns about their child's survival due to their underlying medical issues, feelings of "failure" due to their inability to feed their child orally (16), increased feelings of stress around the tube feeding (17) and decreased support from others due to the tube feeding (18,19). Our research indicates that quality of life can be poor in tube fed children (11), even more so than children with cancer or burns. Given the significance of these issues, the third aim of the study is to examine the effect of the transition from tube to oral feeding on parent stress and parent and child quality of life.

Aim 1: To assess the efficacy of megestrol as part of the 24 week iKanEat protocol.

Hypothesis 1: Children randomized to the megestrol group will be significantly more successful in making the transition to oral feeding (defined as obtaining at least 90% of calories orally) than children randomized to the placebo group.

Aim 2: To assess the safety of 4 weeks of megestrol as part of the 24 week iKanEat protocol.

Hypothesis 2A: Children randomized to the megestrol group will not differ from control children in morning cortisol classification level (low, average, high) and will remain within the normal range at all time points.

Analyses 2B: Exploratory analysis will determine which, if any, covariates (gender, age, and diagnoses at week 0, diagnoses at birth) are related to abnormal morning cortisol levels.

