6.2 Clinic Visit 1 (Week 0)

Participants will be given a full medical history and exam (including vital signs). Height and weight will both be taken in triplicate via calibrated equipment by a trained staff member. Participants taking inhaled or internasal steroids will complete a blood draw (morning cortisol). Participants who are not taking inhaled or intranasal steroids will not complete a blood draw during the Week 0 visit. If an abnormal morning cortisol value is measured, follow the redraw procedures under section 3.4 Primary Safety Endpoints. Participants will bring in a frozen stool sample. Subjects will remain on their current G or G/J tube feeding regimen as determined by their clinical feeding team. If patient is volume sensitive, the feeding team may intervene clinically by placing the subject on continuous feeds when indicated. Families will be encouraged to contact team members with questions or concerns at any time throughout the study period. Participants who complete the measures at pre-screening and complete Clinic Visit 1 will be randomized to an intervention by the study statistician. Participants will be asked measure the child's weight using a digital home weight scale. If the family does not have a digital weight scale, one will be provided to them.

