To address Aim 1, analyses will be conducted using Generalized Linear Mixed Models with a logit link within SAS Proc GLIMMIX to model the binary outcome of transitioned to oral feeding (y/n) defined as at least 90 percent of calories consumed orally. Fixed effects (dummy variables) will be entered for each site as described by McNeish and Stapleton (2016) to account for the clustering of the participants within sites. This will result in essentially, a logistic regression model with appropriate standard errors. Sex, age at initiation, treatment condition, and interactions with treatment condition will enable us to examine the effect of group assignment on successful transition to oral feeding by week 24. Interactions between treatment group and sex will be examined but will not be sufficiently powered to reach definitive conclusions about sex differences. In addition to overall effects, subgroup analyses will be reported for males and females to examine treatment effects within sex groups.

To address Aim 2, we will determine whether any of our participants in either group have adrenal sufficiency levels outside of the normal range at any time point. Should any participant have levels outside of the normal range, we will descriptively examine the individual characteristics associated with this, including group assignment, medical diagnoses, sex, and age at initiation. These characteristics will be reported descriptively.

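### Children on inhaled or intranasal steroids get one more scheduled cortisol draw than the others, before randomization, and the any-time-point rule in Aim 2 counts it

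*Combined protocol and SAP*

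**What the plan says.** Section 3.4 sets the schedule. Morning cortisol "will be drawn at weeks 10 and 14 for all subjects", and "Participants taking inhaled or intranasal steroids will take an additional blood draw at week 0". Section 6.2 confirms that the others are not tested then: "Participants who are not taking inhaled or intranasal steroids will not complete a blood draw during the Week 0 visit".

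Under Planned Analyses in Section 7.1, Aim 2 asks whether participants in either group "have adrenal sufficiency levels outside of the normal range at any time point". It continues: "Should any participant have levels outside of the normal range, we will descriptively examine the individual characteristics associated with this". The list it then gives covers treatment group, diagnoses, sex and starting age. Analyses 2B in Section 2 asks which, if any, "covariates (gender, age, and diagnoses at week 0, diagnoses at birth) are related to abnormal morning cortisol levels".

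Three further points bear on this:

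- Randomization follows completion of Clinic Visit 1 (Section 6.2), and the first dose waits for a normal week 10 result (Section 6.4). Week 0 and week 10 values are therefore both pre-drug.
- Section 3.4 adds that "If an abnormal value is measured, a repeat morning cortisol level will be obtained". Neither Section 2 nor Section 7.1 says whether the first or the repeat value counts for Aim 2.
- Concomitant medications are recorded at every visit (Section 6.11), but steroid use appears in neither list of characteristics.

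**The concern.** A rule that flags a child on any out-of-range value gives more chances to a child who is tested more often. Here the number of scheduled tests depends on a baseline characteristic, inhaled or intranasal steroid use. The analysis neither lists that characteristic nor limits the count to draws that every child has.

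Two things are at stake. First, Aim 2 is meant to describe the safety of four weeks of megestrol, yet a value taken before randomization can put a child among the flagged cases and have that child described by assigned group. Second, if steroid use is more common with some diagnoses than with others, part of any association seen in Analyses 2B would reflect extra testing. A reader could take it as a sign of which children are at risk on the drug.

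**Working it through.** **Plan's own figure.** There is none to reproduce. Section 7.1 gives no power calculation for Aim 2, and the documents state no abnormality rate.

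**Inputs from the documents.** Scheduled draws: 2 for every child, plus 1 for steroid users, so 3 against 2 (Sections 3.4 and 6.2). Sample size: about 60 (Section 3.1).

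**Inputs assumed.** Per-draw probability *a* of an out-of-range value, the same for all children; within-child correlation *rho*; share of children on inhaled or intranasal steroids. The documents give none of these, so ranges are shown.

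**Step 1: independent draws.** The chance of at least one flag in *k* draws is 1 - (1 - *a*)^*k*. At *a* = 0.05:

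- two draws: 1 - 0.95^2 = 0.0975
- three draws: 1 - 0.95^3 = 0.1426
- ratio: 0.1426 / 0.0975 = 1.46

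| *a* | two draws | three draws | ratio |
|---|---|---|---|
| 0.01 | 1.99% | 2.97% | 1.49 |
| 0.05 | 9.75% | 14.26% | 1.46 |
| 0.10 | 19.0% | 27.1% | 1.43 |
| 0.20 | 36.0% | 48.8% | 1.36 |

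**Step 2: correlated draws.** With a beta-binomial model, put *s* = 1/*rho* - 1 and *b* = (1 - *a*)*s*. The chance of no flag in *k* draws is the product over j = 0 to *k* - 1 of (*b* + j)/(*s* + j). For *a* = 0.05 and *rho* = 0.5, *s* = 1 and *b* = 0.95:

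- two draws: 1 - (0.95/1)(1.95/2) = 0.0737
- three draws: 1 - (0.95/1)(1.95/2)(2.95/3) = 0.0892
- ratio: 1.21

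At *rho* = 0.2 the ratio is 0.1184 / 0.0880 = 1.35. At *rho* = 0.8 it is 0.0647 / 0.0595 = 1.09.

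**Step 3: from steroid use to a diagnosis.** If a share *u* of a diagnosis group uses steroids, its chance of a flag is *u* × 0.1426 + (1 - *u*) × 0.0975 (*a* = 0.05, independent draws).

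| users with the diagnosis | users without | flag with | flag without | ratio |
|---|---|---|---|---|
| 20% | 20% | 10.65% | 10.65% | 1.00 |
| 50% | 10% | 12.01% | 10.20% | 1.18 |
| 80% | 10% | 13.36% | 10.20% | 1.31 |
| 100% | 0% | 14.26% | 9.75% | 1.46 |

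**Step 4: children.** The excess per user is 0.1426 - 0.0975 = 0.0451. In 60 children with 10% users this adds 6 × 0.0451 = 0.27 flagged children; with 40% users, 24 × 0.0451 = 1.08. At *a* = 0.10 the excess per user is 0.081, giving 0.49 to 1.94.

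**Step 5: confirmed values only.** If an occasion counts only when an independent repeat is also abnormal, the per-occasion probability at *a* = 0.05 is 0.05^2 = 0.0025. The chances are 1 - 0.9975^2 = 0.50% and 1 - 0.9975^3 = 0.75%. The ratio stays near 1.5, but the absolute excess is very small.

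**Step 6: after the change.** With one post-drug value per child, *k* = 1 for everyone. Both chances equal *a*, and the ratio is 1.00 whatever *a* is.

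**The case against.** The strongest reply is that little rests on this analysis. Section 7.1 treats Aim 2 as descriptive, Section 2 labels Analyses 2B exploratory, and no test or model is specified that could be adjusted for the number of draws. With a handful of flagged children, the week of each abnormal value is known, and medication records show who was on a steroid. All of that stands, and it limits the consequence to interpretation.

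The direction is not guaranteed either. A confirmed abnormal week 0 value pauses the protocol and can lead to removal (Section 3.4). Because randomization comes after that visit, some of these children may never belong to either group. That also stands. It leaves the counting rule unclear but does not equalize the number of draws.

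A reader might infer that the schedule links abnormal cortisol to diagnoses by construction. The documents do not support that. The extra draw is tied to steroid use, and no section says which diagnoses go with inhaled or intranasal steroids or how many children use them. Clustering is plausible, since Section 1.1 names chronic pulmonary disease among the causes of inadequate weight gain, but it is an assumption. Without it, the artefact in the diagnosis comparison is nil.

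**Conclusion.** The point holds in a limited form. The schedule is three draws against two, and the rule in Section 7.1 counts all of them. Steroid users therefore have an additional, pre-randomization chance of being flagged in an aim about megestrol safety. This can distort Analyses 2B; it need not.

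The ratio of 1.46 should not be read as the size of a diagnosis effect. It compares steroid users with non-users under independent draws and an assumed 5% rate. It carries over to a diagnosis only if every child with that diagnosis uses steroids and no other child does. Ratios of about 1.1 to 1.35 between users and non-users with correlated draws, or about 1.18 for a diagnosis with 50% against 10% use, are as consistent with the documents. In absolute terms this is about one child in 60 or fewer at the 5% rate, and up to about two at 10%. One or two children can still matter in a description built on very few cases.

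Nor does the schedule bias the megestrol versus placebo comparison in expectation. Week 0 testing depends on a characteristic fixed before randomization, and assignment is 1:1 within site (Section 5.3).

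The point goes beyond missing detail, because the rule as written mixes unequal pre-drug testing into the outcome.

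**What to change.** In Section 7.1, and by reference for Analyses 2B in Section 2:

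- Base Analyses 2B and the description by characteristic on the post-drug draw. This is the week 14 value or, for children who stop early, the value that Section 5.2 already requires 5 days after the final dose. A literal week 14 rule could omit the children who stopped early, who matter for safety.
- List week 0 and week 10 values separately as pre-drug results. Week 10 belongs there too, since no child has been dosed by then.
- Add inhaled or intranasal steroid use to the characteristics reported. It may itself be related to cortisol, so equalizing the draws does not remove the need to show it.
- Say whether the first or the repeat value decides that a child is abnormal.

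The cost is a few lines of text. No new data are needed, because the draws and the medication records are already planned. The safety draws and their clinical handling do not change.
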